10.5. Prohibited Medications Relevant for Analysis

Prohibited medications as defined in Section 4.4 have been further categorized into groups based on their expected impact on the efficacy variables and planned data handling method:

- **Category 1** – Medications that are not expected to impact efficacy variables (treatment policy)
- **Category 2** – Medications that require blinded adjudication (considering factors such as the type of medication, indication, timing, and frequency) to determine if data should be handled by treatment policy, composite strategy (in the case of medications that are expected to impact efficacy variables and may be indicative of treatment failure), or hypothetical strategy (in the case of medications that are expected to impact efficacy variables but are not indicative of treatment failure)
- **Category 3** – Medications that are expected to impact efficacy variables, but are not indicative of treatment failure (hypothetical strategy)

These categories have been defined separately for the following groups of endpoints:

- CSMS, TNSS, TOSS, DMS and RQLQ(S)+12 endpoints ([Table 7](#))
- Asthma-related endpoints ([Table 8](#))
- SPT endpoints ([Table 9](#))

Table 7: Prohibited medication categories for CSMS, TNSS, TOSS, DMS and RQLQ(S)+12 endpoints

Category 1	Category 2
Treatment policy	Adjudication to determine treatment policy, composite strategy, or hypothetical strategy
1st gen, 2nd gen oral antihistamines/ intranasal antihistamines/ ocular antihistamines	Corticosteroids (intra-muscular/ intra-articular/ extended duration implants such as intravitreal etc)
Longer acting antihistamines (eg, Hydroxyzine/ Cyproheptadine)	Oral/ IV corticosteroids
Topical/ oral decongestants	Systemic calcineurin inhibitors
Intranasal anticholinergics	
SIT with any allergen other than cat
 
Immune directed biologics and/or therapies that would interfere with Type 2 allergic disease or suppress the immune system, including but not limited to anti-IgE, anti IL-5, anti IL-4
 
Specific immunotherapy (SIT) with cat allergen or vaccines against cat allergy

Intranasal corticosteroids	
Ocular corticosteroids	
Ocular/intranasal cromoglycates	
Methylxanthines	
Leukotriene modifiers	

Table 8: Prohibited medication categories for asthma-related endpoints

Category 1 Treatment policy	Category 2 Adjudication to determine Treatment Policy, Composite Strategy, or Hypothetical Strategy	Category 3 Hypothetical Strategy (Multiple Imputation)
1st gen, 2nd gen oral antihistamines/ intranasal antihistamines/ ocular antihistamines	Corticosteroids (intra-muscular/ intra-articular/ extended duration implants such as intravitreal etc)	Inhalational Corticosteroids, SABA/LABA/LAMA if not washed out within timeframes specified in the study protocol
Longer acting antihistamines (eg, Hydroxyzine/ Cyproheptadine)	Oral/ IV corticosteroids	
Topical/ oral decongestants	Immune directed biologics and/or therapies that would interfere with Type 2 allergic disease or suppress the immune system, including but not limited to anti-IgE, anti IL-5, anti IL-4	
Intranasal anticholinergics	Specific immunotherapy (SIT) with cat allergen or vaccines against cat allergy	
Intranasal corticosteroids		
Ocular corticosteroids		
Ocular/intranasal cromoglycates		
Methylxanthines		
Leukotriene modifiers		

Table 9: Prohibited medication categories for SPT endpoints

Category 1 Treatment policy	Category 2 Adjudication to determine Treatment Policy, Composite Strategy or Hypothetical Strategy	Category 3 Hypothetical Strategy (Multiple Imputation)
1st gen, 2nd gen intranasal antihistamines/ ocular antihistamines	Immune directed biologics and/or therapies that would interfere with Type 2 allergic disease or suppress the immune system, including but not limited to anti-IgE, anti IL-5, anti IL-4	1st gen, 2nd gen oral antihistamines (5 day window)
Topical/ oral decongestants	Specific immunotherapy (SIT) with cat allergen or vaccines against cat allergy	Longer acting antihistamines (eg, Hydroxyzine/ Cyproheptadine) (10 day window)
Intranasal anticholinergics		
Intranasal corticosteroids		
Ocular corticosteroids		
Ocular/intranasal cromoglycates		
Methylxanthines		
Leukotriene modifiers		
Corticosteroids (intra-muscular/ intra- articular/ extended duration implants such as intravitreal etc)		
Oral/ IV corticosteroids		
Systemic calcineurin inhibitors		
SIT with any allergen other than cat		

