4.4. Rescue Medication and Prohibited Medication During Study

Medications prohibited throughout the entire study are presented in [Table 2](#) and medications prohibited for specific study periods are presented in [Table 3](#).

Table 2: Medications Prohibited Prior to Screening and Throughout the Study

Medication Group	Time Prohibited Before Study (Washout)
Corticosteroids (intra-muscular/ intra-articular/ extended duration implants such as intravitreal etc.)	Prohibited (3 months)
Tricyclic antidepressants/ typical antipsychotics	Prohibited (14 days)
Specific immunotherapy (SIT) with cat allergen or vaccines against cat allergy	Prohibited (6 months)
SIT with any allergen other than cat	Prohibited
Immune directed biologics and/or therapies that would interfere with Type 2 allergic disease or suppress the immune system, including but not limited to anti-IgE, anti IL-5, anti IL-4	Prohibited (6 months)
Methylxanthines	Prohibited (3 days)
Systemic calcineurin inhibitors	Prohibited (14 days)

Table 3: Medications Prohibited During Specific Periods of the Study

Medication Group	Medication Subgroup	Baseline Assessment Period up to Week 12 and Weeks 48 to 60 (Washout)*
Antihistamines	1 st gen, 2 nd gen oral antihistamines/ intranasal antihistamines/ ocular antihistamines	Prohibited except study provided anti-allergy rescue medications (desloratadine, olopatadine)
	Longer acting antihistamines (e.g., Hydroxyzine/ Cyproheptadine)	Prohibited (10 days)
Decongestants	Topical/ oral	Prohibited (3 days)
Leukotriene modifiers		Prohibited (30 days)
Anti cholinergics	Intranasal anticholinergics	Prohibited (12 h)
Corticosteroids	Intranasal	Prohibited except study provided anti-allergy rescue medications (mometasone nasal spray)
	Ocular	Prohibited (14 days)
	Oral/ IV	Prohibited (30 days)
Cromoglycates	Ocular/ intranasal	Prohibited (14 days)

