* NOTE: Patients will be provided the study rescue medications (desloratadine, olopatadine, mometasone furoate, or in-class equivalent) starting at their baseline assessment visit during screening. Once the patients start their baseline assessment, they should continue to use the study provided rescue medications and avoid any prohibited medications until the completion of the initial efficacy assessment period (weeks 0 to 12). Similarly, the patients should continue to use the study provided rescue medications and avoid any prohibited medications during the final efficacy assessment period (48 to 60 weeks). Prohibited medications (with specific washout durations) are specified in this table for these time periods. Anti-allergic medications (such as antihistamines, anti-allergic eye drops, anti-allergic nasal sprays) outside of study-related anti-allergic medications are prohibited during baseline and efficacy assessment periods (baseline to week 12 and weeks 48 to 60).

Skin prick testing: Antihistamines should be withheld for 5 days prior to SPT (longer acting antihistamines such as hydroxyzine, cyproheptadine should be withheld for 10 days).

Prohibited medications as specified above have been further categorized into groups based on their expected impact on the efficacy variables. Appropriate data handling methods for analysis for each category are described in Section 5.6. Categories of prohibited medications based on their expected impact on efficacy assessment are defined in Section 10.5.

Medications that fall into each of the categories as specified in Section 10.5 are specified in Table 7 (for CSMS, TNSS, TOSS, DMS and RQLQ(S)+12), Table 8 (for asthma-related endpoints), and Table 9 (for SPT endpoints). For medications that fall into Category 2, blinded adjudication by the study medical director will be implemented before the database lock to determine the potential impact of the use of the prohibited medication on the efficacy assessments. The adjudication procedure will be documented.

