5.6.2. Analysis of Secondary Efficacy Variables

The secondary efficacy endpoints will be analyzed using an ANCOVA model in the same fashion as the primary analysis of the primary endpoint.

Average Daily Symptom Score Endpoints (TOSS, TNSS, DMS, TSS)

The average TOSS, TNSS, and DMS will be calculated using all observed daily scores during the specified time period (initial 12 weeks or last 12 weeks of the treatment period).

The average TSS will be calculated by adding average TNSS and average TOSS during the specified time period (initial 12 weeks or the last 12 weeks of the study).

The intercurrent events, strategies, and the corresponding missing data handling approaches for these endpoints will follow the same strategy as for the primary endpoint, outlined in [Table 4](#).

Supplemental analyses using non-parametric methods, such as Wilcoxon ranked sum test or Hodges-Lehmann analysis of median differences, may be performed in the event of a violation of the normality assumption.

Asthma-related endpoints (ADSS, FEV1, ACQ-5)

All asthma endpoints will be analyzed on patients in the FAS with asthma (all randomized patients with ongoing asthma in medical history). Supplemental analyses may be performed in the subset of ongoing asthma patients who were also on asthma medication at baseline.

All available daily ADSS will be averaged over the specified time period (initial 12 weeks or last 12 weeks of the treatment period). If ADSD or ANSD is missing on any given day, ADSS score for that day will be considered missing and no value will be calculated. In addition, ANSD will be shifted by one day, i.e., ADSD on Day 1 and ANSD on Day 2 will be used to get the ADSS on Day 1, ADSD on Day 2 and ANSD on Day 3 will be used to get the ADSS on Day 2, and so on. The day before Visit 6 or Visit 14 for the initial 12 weeks and last 12 weeks, respectively, will be the last day that contributes to the average ADSS (since there will generally be no ANSD measurement corresponding to the date of Visit 6 or 14).

The estimand for ADSS will follow the same approach as for the primary endpoint, described in [Table 4](#). Separate analyses of average ADSD and average ANSD may also be performed.

Estimands for FEV1 and ACQ-5 are specified in [Table 5](#). A supplemental analysis may be performed for the change from baseline ACQ-5 endpoint only in patients with baseline ACQ-5 > 1.5.

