Supplemental analyses using non-parametric methods, such as Wilcoxon ranked sum test or Hodges-Lehmann analysis of median differences, may be performed in the event of a violation of the normality assumption.

Prohibited medications and corresponding data utilization methods relevant for asthma endpoints are specified in [Table 8](#)

SPT endpoints

The intercurrent events, strategies, and the corresponding missing data handling approaches for the SPT endpoints are outlined in [Table 5](#).

Prohibited medications and corresponding data utilization methods relevant for SPT endpoints are specified in [Table 9](#)

Table 5: Summary of Estimands for Secondary Endpoints of Clinical Importance

Endpoint Category	Estimands			
	Endpoint(s)	Population	Intercurrent event(s) handling strategy and missing data handling	Population-level summary
Secondary endpoint – Continuous, SPT, and RQLQ(S)+12	Percent change from baseline to week 12 and end of treatment (week 60) cat SPT mean wheal diameter Change from baseline to week 60 in RQLQ(S)+12	FAS	
The intercurrent events will be handled as follows⁵:
 
 1. Discontinuing the study intervention: all data collected after discontinuation will be used in the analysis (treatment policy strategy) 2. Rescue treatment¹ and select prohibited medications^{2,4} to treat allergic symptoms during the efficacy assessment period: data after allergy-relieving rescue medication will be used in the analysis (treatment policy strategy) 3. Prohibited medications taken during the protocol defined window leading up to the relevant visit (week 12 or week 60) which are adjudicated to be handled using a composite strategy⁴: data will be set to missing and imputed using the worst value of all observations in corresponding treatment group. 	
ANCOVA model with treatment group, stratification factors, and cat sIgE (<17.5 kUa/L versus \geq17.5 kUa/L) as fixed factors and relevant baseline measurement as a covariate.
 
LS-means estimates will be provided for each treatment group, as well as the difference between REGN1908-1909 and placebo with corresponding 95% confidence interval and 2-sided p-value.

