Secondary endpoint – Continuous, FEV1, and ACQ-5	Percent change from baseline to week 12, week 60 FEV1 Change from baseline to week 60 in ACQ-5	FAS with asthma	
 4. Prohibited taken during the protocol defined window leading up to the relevant visit (week 12 or week 60) which are adjudicated to be handled using a hypothetical strategy^{3,4}: data will be set to missing and multiple imputation will be used. 5. Patient does not have exposure to cat leading up to assessment⁶: 
 a. If no cat is living in the patient's home leading up to assessment: all available data will be used in analysis (treatment policy) b. If patient is traveling away from home for less than 42 consecutive days prior to the assessment: all available data will be used in the analysis (treatment policy); otherwise (for travel \geq42 consecutive days), data will set to missing and multiple imputation will be used (hypothetical strategy) 	

Endpoint Category	Estimands			
	Endpoint(s)	Population	Intercurrent event(s) handling strategy and missing data handling	Population-level summary
			
In addition, if a patient has no available value of the relevant measurement at the specified visit, the imputation rules are as follows:
 
 • Missing data because of patients' discontinuation from study due to AEs and lack of efficacy will be imputed using worst score of all the observations in corresponding treatment group • Missing data due to any other reason will be imputed using MI. 	

[1] Note that for SPT endpoints, oral antihistamines are considered as prohibited medication, as specified in [Table 9](#)

[2] Category 1 of [Table 7](#) (RQLQ), [Table 8](#) (asthma), [Table 9](#) (SPT) lists prohibited medications that will be handled using a treatment policy

[3] Additional prohibited medications listed in Category 2 of [Table 7](#), [Table 8](#), and [Table 9](#) will undergo blinded adjudication by study medical monitor before the database lock to determine they will be handled by treatment policy, composite strategy, or hypothetical strategy

[4] Prohibited medications that are not indicative of treatment failure and will be handled by hypothetical strategy are defined in Category 3 of [Table 8](#) and [Table 9](#)

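### SAP Table 8 labels two prohibited drug classes as not expected to affect the asthma endpoints, and Tables 7 to 9 leave some prohibited classes with no category

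*SAP*

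**What the plan says.** SAP Section 4.4 lists the prohibited drugs in Tables 2 and 3 and then states: "Prohibited medications as specified above have been further categorized into groups based on their expected impact on the efficacy variables". Section 10.5 repeats this without exception, says the categories were set separately for three groups of endpoints, and defines three categories:

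- Category 1 is "Medications that are not expected to impact efficacy variables (treatment policy".
- Category 2 goes to blinded adjudication, which may end in treatment policy, a composite strategy or a hypothetical strategy.
- Category 3 is a hypothetical strategy, for drugs expected to affect the endpoint without signalling treatment failure.

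Section 5.6.2 treats "Asthma-related endpoints (ADSS, FEV1, ACQ-5" as one group. It says "Prohibited medications and corresponding data utilization methods relevant for asthma endpoints are specified in" Table 8. Footnote 2 to SAP Table 5 confirms that Category 1 of the relevant table "lists prohibited medications that will be handled using a treatment policy". In Table 8, the last two Category 1 rows are "Methylxanthines" and "Leukotriene modifiers". Its Category 3 holds inhaled corticosteroids and SABA/LABA/LAMA not washed out within the protocol's time frames.

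SAP Table 2 and Protocol Table 1 also prohibit "Tricyclic antidepressants/ typical antipsychotics", with a 14-day washout. That class appears in none of SAP Tables 7, 8 or 9.

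**The concern.** The sorting rule is meant to be specific to the endpoint. Table 9 shows this was intended: oral and longer-acting antihistamines are Category 1 for the symptom scores but Category 3 for the skin prick test. Table 8 gains a Category 3 column, yet its Category 1 list is the symptom-score list carried over unchanged. Two classes with obvious relevance to asthma are therefore described as not expected to affect lung function or asthma control, and no reason is given. Protocol Section 8.2 says that specific prohibited drugs are withheld, including around skin testing and in-clinic spirometry, so that they do not interfere with the procedure.

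The second part concerns completeness. A prohibited class with no category triggers no handling rule. Its data stay in the analysis because nothing removes them, and any other treatment would have to be decided ad hoc near database lock. For tricyclics/typical antipsychotics this gap reaches the primary CSMS estimand through Table 7, and through Table 9 the week 60 cat SPT, which is third in the testing order of SAP Section 5.6.3.

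**Working it through.** The plan gives no figure to reproduce here. The check sets each class prohibited in SAP Section 4.4 against the category lists in Section 10.5.

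**Counting classes.** SAP Table 2 has 7 rows and Table 3 has 9, so 7 + 9 = 16 prohibited classes.

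- Table 7 lists 9 (Category 1) + 6 (Category 2) = 15, and 16 − 15 = 1 is missing.
- Table 8 lists 9 (Category 1) + 4 (Category 2) = 13, and 16 − 13 = 3 are missing. Its Category 3 row concerns inhaled drugs that are not in Section 4.4.
- Table 9 splits oral antihistamines from intranasal and ocular ones, which makes 17 classes. It lists 12 + 2 + 2 = 16, and 17 − 16 = 1 is missing.

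**The classes at issue, by category number.**

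| Class | Section 4.4 | Table 7 (symptom scores, RQLQ) | Table 8 (asthma) | Table 9 (SPT) |
|---|---|---|---|---|
| Methylxanthines | whole study, 3 days | 1 | 1 | 1 |
| Leukotriene modifiers | baseline to week 12 and weeks 48 to 60, 30 days | 1 | 1 | 1 |
| Tricyclics/typical antipsychotics | whole study, 14 days | none | none | none |
| Systemic calcineurin inhibitors | whole study, 14 days | 2 | none | 1 |
| SIT, non-cat allergen | whole study | 2 | none | 1 |

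The nine Category 1 rows of Tables 7 and 8 are the same. Systemic calcineurin inhibitors and non-cat SIT have a category in Tables 7 and 9 but not in Table 8, which looks more like an oversight than a decision.

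**What happens to an unlisted drug.** Section 4.4 sends only Category 2 drugs to adjudication. In SAP Table 4, intercurrent event 2 covers rescue medication and Category 1 drugs, and events 3 and 4 cover drugs adjudicated to the composite or hypothetical strategy. Table 5 has the same structure, with Category 3 added. A drug in no category meets none of these, so its data are used as observed.

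**Which table governs ADSS.** Section 5.6.2 says ADSS follows the approach of Table 4, whose footnotes point to Table 7. It then sends the asthma endpoints, ADSS among them, to Table 8. For methylxanthines and leukotriene modifiers the two routes now agree (Category 1 in both). They already differ for systemic calcineurin inhibitors and non-cat SIT, and an edit to Table 8 alone might not reach ADSS.

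**Would another analysis show the effect?** The worst-score and all-treatment-policy analyses in Section 5.6.1 concern CSMS. Appendix 10.1.1 lists no supportive analysis for the SPT, FEV1, ADSS and ACQ-5 rows. The optional supplements in Section 5.6.2 change the test or the subset, not the handling of prohibited drugs.

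**The case against.** Treatment policy is a legitimate, prespecified strategy. Under it, on-drug values belong to the estimand, and calling them contaminated presumes a different estimand. SAP Section 1.2.5 lists the updated Tables 7 to 9 among the major changes of an amendment made mainly in response to regulatory feedback on intercurrent events. This stands. What remains open is the stated reason for Category 1 and the incomplete mapping, not treatment policy as such.

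The contrast with inhaled drugs is also weaker than it first looks. The bronchodilator washouts in Protocol Section 9.2.2.10 are examples tied to spirometry, and they name neither methylxanthines nor leukotriene modifiers. But both classes carry washouts elsewhere in the same plan, so the label still needs a reason.

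A reader might infer that tricyclics shrink the wheal and that a suppressed wheal would then pass as a treatment response. The documents do not support this. The skin-test withholding rule names only antihistamines (5 days, or 10 for longer-acting ones), Table 9 Category 3 mirrors it, and the 14-day entry is a general prohibition with no stated link to wheal size. Nothing suggests that use would differ by arm.

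A reader might also want a bias in ACQ-5 points. That would need usage rates by arm and drug effects, and the documents give neither.

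Finally, exposure should be limited. Exclusion criterion 9 bars patients taking prohibited treatment, Protocol Section 8.3.2.2 calls for contact with the medical monitor if such a drug is needed, and SAP Section 5.3 tabulates prohibited use. Oral and IV corticosteroids already go to adjudication in Table 8. All of this stands and keeps the point minor.

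**Conclusion.** The point holds as a minor defect in two parts. First, Table 8 assigns methylxanthines and leukotriene modifiers to a category whose definition does not fit their prohibited status, and it does so by repeating a list drawn up for other endpoints. Second, the SAP says the Section 4.4 drugs have been categorised, but one class is missing from all three tables and two more are missing from Table 8.

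The size of any bias cannot be derived from the documents and is probably small. The pool for the asthma endpoints is at least 0.30 × 630 = 189 patients, from the expectation in Protocol Section 1 that at least 30% will have asthma. That is the size of the analysis set, not the number of users. None of the 13 steps in the testing hierarchy is an asthma endpoint, so the Table 8 labels cannot change a confirmatory conclusion. The tricyclic gap does touch the first and third steps, but only as a missing rule; no effect on either endpoint is shown.

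One assumption lies outside the documents: that methylxanthines and leukotriene modifiers can affect asthma measures is general pharmacology. It supports sending them to adjudication, not any particular outcome of it.

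**What to change.** Before database lock, under the blinded revision that SAP Section 1 allows:

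1. In Table 8, move methylxanthines and leukotriene modifiers to Category 2. The adjudication is already planned and can still end in treatment policy.
2. State in Section 5.6.2 that ADSS uses Table 8 for prohibited drugs, and reconcile this with the reference to Table 4. Say at the same time whether the Category 3 row, which is keyed to spirometry washout, applies to diary and questionnaire scores.
3. Give every Section 4.4 class an explicit category in each of Tables 7, 8 and 9. This means tricyclics/typical antipsychotics in all three, and systemic calcineurin inhibitors and non-cat SIT in Table 8. For tricyclics/typical antipsychotics in Table 9, reconcile the category and any analysis window with the prohibition in SAP Table 2.

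The cost is edits to three tables and one paragraph, plus a few more records for adjudication. No new data are needed, and sample size and alpha are untouched.

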\*NOTE: Patients will be provided the study rescue medications starting at their baseline assessment visit during screening. Once the patients start their baseline assessment, they should continue to use the study provided rescue medications and avoid any prohibited medications until the completion of the initial efficacy assessment period (weeks 0 to 12). Similarly, the patients should continue to use the study provided rescue medications and avoid any prohibited medications during the final efficacy assessment period (48 to 60 weeks). Prohibited medications (with specific washout durations) are specified in this table for these time periods. Anti-allergic medications (such as antihistamines, anti-allergic eye drops, anti-allergic nasal sprays) outside of study-related anti-allergic medications are prohibited during baseline and efficacy assessment periods (baseline to week 12 and weeks 48 to 60).

Skin prick testing: Antihistamines should be withheld for 5 days prior to SPT (longer acting antihistamines such as hydroxyzine, cyproheptadine should be withheld for 10 days)

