## 11.4.3. Efficacy Analyses

#### 11.4.3.1. Primary Efficacy Analysis

The primary endpoint, the daily CSMS averaged over the last 12 weeks of the treatment period (weeks 48 to 60), will be analyzed on the full analysis set (FAS), which consists of all randomized patients.

The primary analysis will focus on the comparison between REGN1908-1909 and placebo in the FAS. The analysis will be performed using an analysis of covariance (ANCOVA) model, with the treatment group, randomization stratification factors, and cat sIgE (<17.5 kUa/L versus ≥17.5 kUa/L) as fixed effects and the baseline CSMS as a covariate. The least squares means estimates for the average CSMS during the last 12 weeks of the treatment period for each treatment group, as well as the difference between the REGN1908-1909 and placebo will be provided along with the corresponding 2-sided p-value and associated 95% confidence interval.

Only days with observed data will be included in the calculation of average score. The average CSMS (max score 38/day) will be calculated based on the sum of daily total nasal symptom scores (TNSS, max score 12/day), daily TOSS (max score 6/day) and daily medication scores (DMS, max of 20/day) recorded over the last 12 weeks of the treatment period (weeks 48 to 60).

Any data collected after rescue medication use will be used in the analysis for the CSMS. Since the relevant prohibited medication use may have an impact on symptom measurements, the CSMS data will be set to missing at the time of and after receiving the prohibited medication. The details of the relevant prohibited medications will be specified in the SAP. The primary estimand will

utilize the CSMS calculated by observed components prior to receiving relevant prohibited medication or the worst score of all observations in corresponding treatment group if a patient has no single value of CSMS during the last 12 weeks of the treatment period (composite strategy).

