4.5.5. Definitions

The definition and details of the efficacy variables are listed as follows:

Total Nasal Symptom Score (TNSS)

The TNSS ranges from 0 to 12 and is based on assessment of 4 nasal symptoms graded on a Likert scale ranging from 0 (none) to 3 (severe) for nasal congestion, itching, and runny nose, and sneezing. The TNSS will be recorded before going to bed for the night using an e-diary.

Total Ocular Symptom Score (TOSS)

The TOSS ranges from 0 to 6 and is based on 2 eye symptoms: itching/redness/gritty feeling and tearing/watering. Each of the 2 symptoms is graded on a Likert scale ranging from 0 (none) to 3 (severe). The TOSS will be recorded before going to bed for the night using an e-diary.

Total Symptom Score (TSS)

The daily TSS is calculated by adding the TNSS and TOSS together, for a combined TSS of 0 to 18.

Daily Medication Score (DMS)

For the DMS, before going to bed for the night, patients will be asked to record their daily rescue medication use using an e-diary, including which medications and the amount of these pre-specified medications. This information will be used to calculate the DMS for the following medications or the approved in-class equivalents, as follows: desloratadine 5 mg 6 points/dose; maximum daily score 6 points, olopatadine 1 mg/mL each drop 1.5 points/drop; maximum daily score 6 points, mometasone furoate 50 ug/dose 2.0 points/spray; maximum daily score 8 points). The maximum DMS score is 20 (Calderon, 2014).

Combined Symptom and Medication Score (CSMS)

The daily CSMS is calculated by adding the DMS and TSS together, with scores ranging between 0 and 38. The method for calculating average CSMS is described in Section [5.6.1](#).

Skin Prick Test

An SPT with cat allergen extract, other relevant allergens, a negative control (such as saline/diluent), and a histamine positive control will be performed to assess sensitization status. A positive response for cat is defined by a mean wheal diameter (MWD) at least 5 mm greater than a negative control, in which SPT MWD is defined as $([\text{longest diameter} + \text{longest perpendicular}]/2)$. (Note: For other allergens, a positive sensitization is defined as a MWD of at least 3 mm greater than a negative control.)

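### Non-study oral antihistamines, antihistamine eye drops and nasal steroids are classed as not expected to affect CSMS, yet these three classes supply all 20 DMS points and no rule scores them when they replace study drug

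*SAP*

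**What the plan says.** **Classification.** SAP 10.5 defines Category 1 as "Medications that are not expected to impact efficacy variables (treatment policy"). Data after such use are kept and no adjudication takes place. Table 7, which governs CSMS, TNSS, TOSS, DMS and RQLQ(S), lists in Category 1 "1st gen, 2nd gen oral antihistamines/ intranasal antihistamines/ ocular antihistamines" and, as separate entries, "Intranasal corticosteroids" and "Ocular corticosteroids".

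**Scoring.** SAP 4.5.5 builds the DMS from "desloratadine 5 mg 6 points/dose; maximum daily score 6 points, olopatadine 1 mg/mL each drop 1.5 points/drop; maximum daily score 6 points", plus mometasone nasal spray at 2.0 points per spray up to 8. Points are computed for these three products or approved in-class equivalents, and the diary asks only about those pre-specified drugs. Protocol 8.2 makes an equivalent subject to sponsor agreement. No rule covers an unapproved product of a scored class.

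**Intercurrent events.** SAP Table 4, event 2, groups the Category 1 drugs with rescue treatment, as medication used for allergic symptoms, and applies treatment policy.

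**Prohibition.** The note to Protocol Table 2 (section 8.9.1) says that anti-allergic products "outside of study-related anti-allergic medications are prohibited during baseline and efficacy assessment periods". Protocol 11.4.3.1 sets CSMS to missing after certain drugs, reasoning "Since the relevant prohibited medication use may have an impact on symptom measurements", and leaves the list of those drugs to the SAP.

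**The concern.** The CSMS is meant to capture both symptoms and the medication needed to control them. A patient who takes a non-study oral antihistamine instead of desloratadine has the symptom score lowered by the drug and records no DMS points for it. On that day the score no longer reflects medication need, which is part of the primary objective. The Category 1 label gives a reason for accepting this that does not fit the endpoint: the same classes are worth up to 20 points when the product is study-supplied.

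Such use is plausible. Entry requires rescue use on at least 8 of 15 baseline days, so these patients use the scored classes regularly. The Table 2 restrictions on them run from baseline to week 12 and from week 48 to week 60. Between weeks 12 and 48 they are not in force, so a patient using another product must switch back just as the primary window opens. The SAP itself plans for such use with an intercurrent-event rule and dedicated tables.

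At stake is the size of the primary difference, and its direction of error is not fixed. More unscored use on placebo dilutes the effect; more on active inflates it.

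**Working it through.** **1. Points by class (SAP 4.5.5, Table 7).**

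| Category 1 class | Maximum daily DMS points if study-supplied or approved |
|---|---|
| Oral antihistamine | 6 |
| Ocular antihistamine | 6 |
| Intranasal corticosteroid | 8 |
| Intranasal antihistamine | 0 (none supplied or scored) |
| Ocular corticosteroid | 0 (none supplied or scored) |

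DMS maximum = 6 + 6 + 8 = 20. TSS maximum = 12 + 6 = 18. CSMS maximum = 18 + 20 = 38, and 20/38 = 52.6%. The plan's maxima reproduce, and the first three classes account for every DMS point.

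**2. The plan's sample size (SAP 2.3).** Inputs: difference 1.8, SD 6.2, two-sided alpha 0.049, power 90%. With n = 2(z₁₋α/₂ + z₀.₉₀)² × SD² / difference², n = 251 per arm, as stated. Exact noncentral-t power at 251 per arm is 89.9%.

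**3. One substituted day.** Replacing one scored desloratadine dose with an unscored oral antihistamine lowers that day's CSMS by 6 points. 6 / 1.8 = 3.3 times the planned difference.

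**4. Shift in the treatment difference.** Shift = points lost per day × between-arm excess in the share of patient-days with full substitution. For an oral antihistamine, one percentage point gives 6 × 0.01 = 0.06.

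**5. Effect on power.** The excesses are assumptions, since the documents give no rate. Also assumed: full substitution, symptoms the same as on study drug, SD 6.2, 251 per arm, alpha 0.049.

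| Placebo excess (percentage points of days) | Shift | Remaining difference | Power |
|---|---|---|---|
| 0 | 0 | 1.80 | 89.9% |
| 1 | 0.06 | 1.74 | 87.9% |
| 2.5 | 0.15 | 1.65 | 84.3% |
| 5 | 0.30 | 1.50 | 76.9% |

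For a nasal steroid at the full 8 points, a 5-point excess gives 8 × 0.05 = 0.40, a remaining difference of 1.40 and power of 71%. Removing the whole 1.8 would take an excess of 1.8/6 = 30% of days for the oral antihistamine, or 1.8/8 = 22.5% for the nasal steroid.

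**6. The other direction.** If the drug had no effect and the active arm had a 5-point excess of oral-antihistamine substitution, the same 0.30 would appear as benefit. The test would then reject with probability 8.3%, against 4.9% nominal.

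**7. Whether another analysis covers this.** The supplemental analysis that applies treatment policy to every event (SAP 5.6.1) leaves the scoring unchanged. The worst-score and worst-5th-percentile imputations in the same section apply after relevant prohibited medication, without saying whether Category 1 counts. Even if it does, they impute a poor score; they do not add medication points.

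**The case against.** **Treatment policy is deliberate and legitimate.** SAP 1.2.5 says the prohibited-medication strategy was updated on regulatory feedback, with the Table 7 categories among the changes, and event 2 in Table 4 does not depend on the Category 1 wording. This stands. A reader might infer that treatment policy is itself the error, but the documents do not support that. The faults are the stated reason and the silence on scoring.

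**The protocol does not contradict Table 7 directly.** Section 11.4.3.1 concerns relevant prohibited drugs and leaves the list to the SAP, and the Table 2 note gives no reason for the prohibition. This also stands. The inconsistency lies within the SAP, between the Category 1 label on one side and the DMS definition and event 2 on the other. Table 9 points the same way for a different endpoint: it treats oral antihistamines as expected to affect the skin prick test.

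**Loss of points needs replacement, not addition.** A patient who adds a non-study antihistamine to one desloratadine dose still scores the capped 6. All three classes are supplied for use as needed, and unapproved use is a deviation. A reader might take every non-study dose as 6 or 8 points lost; that is too strong.

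**Scoring from the concomitant-medication record could add error.** SAP 6.4 imputes incomplete end dates late, so one as-needed entry could add points for weeks. The documents do not show that the record holds daily drop or spray counts, and an antihistamine may be taken for another reason. This is a good argument against changing the primary derivation, but not against a sensitivity analysis.

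**Use is already tabulated.** SAP 5.3 summarises prohibited medications, possibly by 12-week period. That shows who took them but not what they do to the CSMS.

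**Conclusion.** The point holds for three classes: oral antihistamines, ocular antihistamines and intranasal corticosteroids. Followed as written, the SAP lets unapproved products of these classes enter the primary score without medication points, under a rationale that the CSMS construction contradicts. Up to 6, 6 or 8 points are lost on a fully substituted day.

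The size in the trial is unknown. The 0.06 per percentage point is arithmetic under full substitution and unchanged symptoms; the power figures of 88%, 84% and 77% depend on assumed between-arm excesses and are not forecasts.

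Four stronger readings should be resisted.

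- That the SAP states these drugs score zero: it does not. Zero follows from the DMS definition and the absence of a rule, and sponsor-approved equivalents do score.
- That all the listed antihistamines and steroids carry points: ocular steroids and intranasal antihistamines carry none.
- That the handling favours the drug: the direction depends on which arm uses more.
- That medicated days will count as exploratory well days: this follows only if rescue medication in that definition means study-supplied drugs alone.

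**What to change.** 1. Keep treatment policy and the diary-based DMS for the primary analysis.
2. Reword the Category 1 rationale in SAP 10.5 so that it no longer says these three classes are not expected to affect CSMS or DMS. State that their data are kept under treatment policy as part of the estimand, in line with event 2 of Table 4.
3. State explicitly that unapproved products of the scored classes earn no points in the primary DMS.
4. Pre-specify a sensitivity analysis of the primary endpoint, and of DMS in weeks 48 to 60, that adds in-class points for each recorded day of non-study oral antihistamine, ocular antihistamine or intranasal corticosteroid use for allergic symptoms. Cap the daily class totals at the existing 6, 6 and 8. Give the analysis its own rule for incomplete dates and doses, because the late end-date convention in SAP 6.4 would overcount. TNSS contains no medication points, so rescoring leaves it unchanged.
5. Report days of such use by arm and class in weeks 48 to 60.
6. Say whether the worst-score analyses in SAP 5.6.1 include Category 1 drugs.

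The cost is SAP wording and one derivation from data already collected (medications are recorded from consent to end of study), settled on blinded review before lock. The downside is that concomitant-medication dates and doses are coarser than the e-diary, which is why this is a sensitivity analysis and not the primary derivation.
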